#### 8.5.2 After 8 Weeks Post-SRT

Only AEs requiring that the PD-1 or PD-L1 inhibitor be discontinued **and** that steroids be administered will be recorded beginning after the 8-week post-SRT AE assessment.

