### **2.2 Secondary Objectives**

In patients who have received study treatment (SRT and PD-1/PD-L1 inhibitor):

- 2.2.1 To determine the response rate of SRT and PD-1/PD-L1 inhibiting therapy per unidimensional immune-related response criteria (irRC) and, if brain metastases are present, per iRANO
- 2.2.2 To determine the response rate at irradiated tumor sites
- 2.2.3 To determine the response rate at non-irradiated tumor sites
- 2.2.4 To determine the 2-year survival rate
- 2.2.5 To assess the toxicity associated with the study treatment
- 2.2.6 To assess the radiobiological and immunological characteristics of patients receiving study treatment using blood samples collected before and after SRT

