#### 6.7.1.2 AEs Related to PD-1 or PD-L1 Inhibiting Therapy

Assessment and reporting of selected AEs related to the PD-1 or PD-L1 inhibiting therapy as described in Section [8.5.2](#) will continue until the PD-1 or

PD-L1 inhibitor has been discontinued (for any reason) or until 2 years after completion of SRT, whichever occurs first.

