### 8.2.1 Lung (Central and Peripheral), Mediastinal/Cervical Lymph Node Metastases

- Cardiac and pericardial injury  
Cardiac and pericardial injury is uncommon in the conventionally-fractionated course of RT, side effects can be seen with large doses per fraction of SRT.
- Gastrointestinal/Esophageal injury  
Esophagitis (ie, dysphagia causing pain on swallowing) relatively soon after SRT is completed; typically resolves on its own within days to a week or longer
- Central Airway/Bronchial injury  
Bronchial toxicity includes:
  - Cough
  - Dyspnea
  - Hypoxia
  - Pleural effusion
  - Pleuritic pain associated with collapse
  - Bronchial necrosis/fistula
  - Hemoptysis/pulmonary hemorrhage
- Lung injury  
Radiation pneumonitis (ie, inflammation of the end bronchioles and alveoli); toxicities include:
  - Fever
  - Shortness of breath
  - Pulmonary infiltrate on chest x-ray

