#### 8.2.3 Spinal Metastases

- Radiation myelitis
- Radiation esophagitis
- Radiation laryngitis or pharyngitis
- Radiation pneumonitis

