### 8.5 Time Period and Grade of AE Capture

#### 8.5.1 From Initiation of SRT Until 8 Weeks Post-SRT

All SRT-related and immunotherapy-related **≥ grade 3** AEs will be recorded beginning at the time of the first SRT fraction and continuing until 8 weeks following completion of SRT.

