**Table 1. Expedited Reporting Requirements**

SAEsA	UPsB
Principal InvestigatorC [name] [REDACTED]	Principal InvestigatorC [name] [REDACTED]
Study TeamC [name], BSN [REDACTED]	Study TeamC [name], BSN [REDACTED]
	DSMCD [REDACTED]
	IRBE

A. Refer to Section 8.1.2 for SAE definition. After the 8-week post-SRT assessment, only AEs meeting the criteria outlined in Section 8.5.2 will be recorded; if the AE is an SAE, the event will be reported in an expedited manner as noted on this table.
 
B. Refer to Section 8.1.3.
 
C. Report event within 1 business day of becoming aware of the occurrence.
 
D. Report event within 2 business days of becoming aware of the occurrence.
 
E. Report each UP to the VCU IRB within 5 business days of becoming aware of the occurrence.
	

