### 13.4 Statistical Analysis of Secondary Objectives

Patients' demographics, AEs and SAEs, disease status, treatment status, clinical response, etc will be listed and summary descriptive statistics will be calculated. Rate of higher grade AEs will be reported at each follow-up visit.

Time to death, time to progression at the irradiated site, and time to progression at a non-irradiated site will be summarized using the Kaplan Meier survival curve. Overall survival probabilities will be estimated with 95% confidence intervals at each follow-up time point during the 2-year follow-up. Analysis of the secondary objectives will include all evaluable patients; however, a subset analysis of evaluable patients who only receive SRT to brain metastases will also be performed.

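### After week 8 post-SRT, routine AE recording is limited to events needing both inhibitor discontinuation and steroids, so late grade 3+ SRT toxicity is largely uncaptured and later per-visit AE rates are biased low

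*Combined protocol and SAP*

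**What the plan says.** Objective 2.2.5 is "To assess the toxicity associated with the study treatment". It has no time limit and is not confined to immunotherapy.

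Recording has two windows.

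- **To week 8 (Section 8.5.1).** For SRT-related and immunotherapy-related events of grade 3 or higher, "AEs will be recorded beginning at the time of the first SRT fraction and continuing until 8 weeks following completion of SRT".
- **After week 8 (Section 8.5.2).** "Only AEs requiring that the PD-1 or PD-L1 inhibitor be discontinued" are recorded, and only if steroids are also given. Table 5 note D repeats this for weeks 16, 24 and 52. Note E limits year 2 AE assessment to patients still on the inhibitor.

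Section 6.7.1.2 ends the late window once the "PD-L1 inhibitor has been discontinued (for any reason) or until 2 years after completion of SRT, whichever occurs first". Table 1 note A carries the filter into SAE reporting: "After the 8-week post-SRT assessment, only AEs meeting the criteria outlined in Section" 8.5.2 are recorded, and an SAE is expedited only if it is among them.

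The AE endpoint (3.4.5) follows the same two windows, and its late part covers immunotherapy-related events only. Section 13.4 nevertheless states: "Rate of higher grade AEs will be reported at each follow-up visit". Section 8.6 says, without a time limit, that all AEs, SAEs and unanticipated problems go into OnCore.

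**The concern.** SRT is the component this trial adds, since patients continue an inhibitor they were already receiving. Yet no window after week 8 is aimed at SRT toxicity. The two late conditions, stopping the inhibitor and giving steroids, describe how an immune-related event is handled. Section 8.2 lists SRT risks such as "Bronchial necrosis/fistula", "Radiation myelitis", pulmonary haemorrhage and liver failure, and none of these has to meet both conditions. Once the inhibitor has stopped, an event can no longer require it to be stopped.

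The protocol itself treats late and uncertain toxicity as relevant. Section 1.9.2 cites the department's work on late normal-tissue effects. Section 6.3.4 says the toxicity of SRT to several metastases close to earlier radiation volumes is unknown. Section 1.10 widened eligibility partly because the combination appeared to be low risk.

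At stake is the safety summary for weeks 16, 24, 52 and year 2. It would look favourable partly because of the recording rule. Section 13.3 sends all secondary endpoints to the DSMC at the end of stage 1, when patients have reached week 24, so that summary would already carry the filter.

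**Working it through.** The plan states no figure for this point, so the check sets the sections side by side and then sizes the gap.

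**1. Capture rule at each follow-up point (Table 5 with 8.5.1, 8.5.2 and 6.7.1.2)**

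| Follow-up point | What is recorded | Complete grade 3+ rate possible? |
|---|---|---|
| Week 4 | All related grade 3+ AEs | Yes |
| Week 8 | All related grade 3+ AEs | Yes |
| Weeks 16, 24, 52 | Only AEs needing discontinuation and steroids | No |
| Year 2 | Same filter, and only patients still on the inhibitor | No |

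The rate in 13.4 is complete at 2 of 6 points and incomplete at 4 of 6.

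**2. Direction of the bias.** Section 13.4 analyses secondary objectives in all evaluable patients. The filter can remove a grade 3+ event from the numerator but cannot add one, and the denominator stays the same. As a measure of all related grade 3+ events, the later rates can only be too low.

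**3. Share of follow-up with full capture**

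- Post-SRT time only: 8/104 = 7.7%. The other 96/104 = 92.3% is restricted.
- Counting the SRT course, since recording starts at the first fraction, and taking 1 to 3 weeks for SRT (6.3.3 allows up to 3): (8+1)/(104+1) = 8.6% to (8+3)/(104+3) = 10.3%.

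These are shares of calendar time, not of risk.

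**4. Consistency among the capture sections**

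- 8.6 against 8.5.2: all AEs and SAEs are recorded, or only the filtered ones.
- 3.4.5 against 6.7.1.2: the late window runs to 2 years, or ends earlier when the inhibitor stops. Section 6.4.4 makes 12 months the default inhibitor course, so a patient who stops then has no AE capture in year 2.
- 8.5.2 against 3.4.5 and 6.7.1.2: 8.5.2 sets no attribution limit, while the other two confine the late part to immunotherapy-related events.

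**5. Illustration with assumed rates.** The documents give no late SRT event rate and no share of such events that would meet the rule. Let q be the share of patients with a late grade 3+ SRT event and f the share of those events meeting both conditions. Use n = 42, the evaluable target in 13.2, as a stand-in for the safety population.

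- Expected events = 42q. For q from 5% to 15%: 42 × 0.05 = 2.1 to 42 × 0.15 = 6.3.
- Expected recorded = 42qf. For f from 0% to 50%: 0 to 6.3 × 0.5 = 3.15.
- Chance that none is recorded = (1 − qf)^42. At q = 10% and f = 25%: 0.975^42 = 0.345.
- Over q from 5% to 15% with f from 25% to 50%, that chance runs from 59% (q = 5%, f = 25%) to 4% (q = 15%, f = 50%). With f = 0 it is 100%.

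**The case against.** The strongest defence is that this is a deliberate choice of scope. Endpoint 3.4.5 puts objective 2.2.5 into practice with the same two windows, so the endpoint and the data collected largely match. The protocol gives reasons for light monitoring: SRT is standard treatment (6.2, 6.3), toxicity of the combination is described as similar to monotherapy (1.10), and the safety profile is called established (3.2). The conflict with 13.4 could be removed by narrowing that one sentence.

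This stands against two stronger readings that a reader might infer.

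- **That the toxicity objective or the per-visit rates cannot be met at all.** The documents do not support this. Endpoint 3.4.5 can be reported as written, and complete rates exist at weeks 4 and 8.
- **That late severe SRT events leave no record and stay hidden from the DSMC.** This is too absolute. Section 8.6 read literally requires a record, so the documents contradict each other. Unanticipated problems go to the DSMC within 2 business days, and the week 8 limit in Table 1 sits in the SAE column only. Secondary malignancies are expedited with no stated time limit (8.4). Deaths are seen through 2-year vital status, though without AE attribution. The reason for stopping treatment is documented (6.6). An SRT event that met both conditions would also fit the wording of 8.5.2.

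These routes do not close the gap. A toxicity already listed in 8.2 will often not be unexpected in nature, so it need not qualify as an unanticipated problem. Vital status does not count non-fatal events. Narrowing 13.4 would make the plan consistent but would still leave late SRT toxicity unmeasured.

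**Conclusion.** The point holds in a limited form. After week 8, grade 3+ SRT-related events that do not lead to both inhibitor discontinuation and steroids, or that occur after the inhibitor has stopped, are largely outside routine recording. Objective 2.2.5 is then only partly assessed. The 13.4 rates would be incomplete and biased low at 4 of 6 follow-up points, and 8.6 contradicts 8.5.2.

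These conclusions rest on the text alone. The number of events lost is not known. Section 8.2 gives no onset times for fistula, haemorrhage, myelitis or liver failure, so the 2.1 to 6.3 expected events and the 0 to 3.15 recorded depend on the assumed 5% to 15% rate and 0% to 50% share meeting the rule. Nothing here affects the primary efficacy endpoint.

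**What to change.** - **Capture.** In 3.4.5, 6.7.1, 8.5.2, Table 1 note A and Table 5 notes D and E, record all SRT-related or immunotherapy-related grade 3+ AEs and related SAEs at the scheduled follow-up contacts through 2 years, whether or not the inhibitor continues or steroids are given.
- **Vital-status follow-up.** For patients followed for survival only after progression (Table 5 note S), limit this to related grade 3+ events that become known at those contacts.
- **Reconciliation.** Align 8.6 with 8.5.2, and make the end date and attribution rule the same in 3.4.5, 6.7.1.2 and 8.5.2.
- **Analysis.** In 13.4, summarise late SRT toxicity separately and state which capture rule applies to each visit's rate.

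If the sponsor keeps the present capture, the minimum is to reconcile 8.6 and to limit objective 2.2.5 and the 13.4 sentence to what is collected, naming late SRT toxicity as not assessed.

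The change concerns data collection only and alters no treatment rule. Table 5 already schedules AE assessment at weeks 16, 24 and 52. The cost is modest extra data entry. It is somewhat greater in year 2 for patients off the inhibitor, who have no AE assessment now, and attribution will be harder after progression or new therapy.

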### 8.6 Procedures for Recording AEs, SAEs, and UPs

All AEs, SAEs, and UPs will be recorded in MCC's OnCore Clinical Trials Management System. In most cases, it is acceptable to record in OnCore only the highest grade of a toxicity occurring during a particular study segment when an event has serial fluctuations in grade over time.

SAE's will be entered into the OnCore SAE domain. UPs will be entered into the OnCore Deviations domain. An SAE that is both an SAE and a UP will be entered in both domains. For all SAEs, a corresponding entry should be made in the routine AE record to match the event entries in the SAE domain.

### 8.7 Expedited Reporting Procedures

Refer to [Table 1](#) for expedited reporting requirements and instructions.

**Table 1. Expedited Reporting Requirements**

SAEsA	UPsB
Principal InvestigatorC [name] [REDACTED]	Principal InvestigatorC [name] [REDACTED]
Study TeamC [name], BSN [REDACTED]	Study TeamC [name], BSN [REDACTED]
	DSMCD [REDACTED]
	IRBE

A. Refer to Section 8.1.2 for SAE definition. After the 8-week post-SRT assessment, only AEs meeting the criteria outlined in Section 8.5.2 will be recorded; if the AE is an SAE, the event will be reported in an expedited manner as noted on this table.
 
B. Refer to Section 8.1.3.
 
C. Report event within 1 business day of becoming aware of the occurrence.
 
D. Report event within 2 business days of becoming aware of the occurrence.
 
E. Report each UP to the VCU IRB within 5 business days of becoming aware of the occurrence.
	

## 9 PHARMACEUTICAL INFORMATION

[REDACTED]

[REDACTED]

[REDACTED]

[REDACTED]

[REDACTED]

[REDACTED]

[REDACTED]

[REDACTED]

[REDACTED]

## 10 MEASUREMENT OF EFFECT

### 10.1 Criteria for Tumor Response

Objective criteria will be used to assess tumor response in this study. RECIST v1.1 and unidimensional irRC will be used at each assessment time point. RANO-BM and iRANO criteria will be used to determine tumor response in the brain, if the brain metastases were treated with SRT. The criteria to be used for tumor response-related endpoint analyses are as follows:

- RECIST v1.1 ([94](#))
- RANO-BM Criteria for patients with brain metastasis ([95](#))
- Unidimensional irRC ([96](#)) modified to permit use of short-axis measurement for lymph nodes, in line with RECIST v1.1; also refer to [Table 2](#)
- iRANO criteria for patients with brain metastasis ([97](#)); also refer to [Table 3](#)

**Table 2. Unidimensional Immune-Related Response Criteria**

Guidelines	
New, measurable (ie, $\geq 10$ mm) lesions	Incorporated into tumor burden A
New, nonmeasurable lesions	Do not define progression (but preclude irCR)
Non-index lesions	Contribute to defining irCR (complete disappearance required)
Response	Criteria
Complete Response (irCR)	Disappearance of all lesions in 2 consecutive observations not less than 4 weeks apart
Partial Response (irPR)	$\geq 30\%$ decrease in tumor burden compared with baseline in 2 observations at least 4 weeks apart
Stable Disease (irSD)	Does not meet criteria for irCR, irPR, or irPD
Progressive Disease (irPD)	At least 20% increase in tumor burden compared with nadir (at any single time point) in 2 consecutive observations at least 4 weeks apart
A. Tumor Burden = the sum of unidimensional diameters of targets and new lesions	

**Table 3. RANO-BM and iRANO Criteria for Brain Metastasis**

Response	RANO-BM Criteria*
Complete Response	Disappearance of all CNS target lesions for $\geq 4$ weeks; disappearance of all enhancing CNS non-target lesions; no new lesions; no steroids; clinically stable or improved
Partial Response	$\geq 30\%$ decrease in sum of longest diameters of target lesions for $\geq 4$ weeks; no new lesions; stable or decreased steroid dose; clinically stable or improved
Stable Disease	Does not qualify for complete response, partial response, or progressive disease
Progressive Disease	$\geq 20\%$ increase in the sum of longest diameters of target lesions; and at least one lesion must increase by an absolute value of 5 mm or more; or unequivocal progression of existing enhancing non-target CNS lesions; or new lesions; or unequivocal progression of existing tumor-related non-enhancing (T2/FLAIR) CNS lesions
*iRANO recommends confirmation of disease progression on follow-up imaging 3 months after initial radiographic progression if there are no new or substantially worsened neurological deficits that are not due to comorbid events or concurrent medications and if the patient's duration on the current immunotherapy regimen is 6 months or less. For this trial, that 6-month window will begin with the initiation of protocol therapy and not that patient's first exposure to immunotherapy. If follow-up imaging confirms disease progression, the date of actual progression should be back-dated to the date of initial radiographic progression. The appearance of new lesions 6 months or less from the initiation of protocol therapy alone does not define progressive disease.	

## 10.2 Tumor Response Requirements

### 10.2.1 Time Points for Assessment of Tumor Response

Objective disease assessment will be performed at the following time points:

- At baseline (before SRT begins)
- At 8 weeks (+/- 2 weeks) after the last SRT fraction
- At 16 weeks (+/- 2 week) after the last SRT fraction
- At 24 weeks (+/- 2 week) after the last SRT fraction
- If needed, at approximately 28 weeks (at least 4 weeks after the 24-week tumor response assessment), an additional objective disease assessment may be performed to confirm response status

At the investigator's discretion, additional assessments may be performed when clinically indicated.

### 10.2.2 Imaging

Only imaging of the initial sites of disease is required at subsequent time points to provide tumor measurements for assessment of antitumor effect. The same type of imaging used at baseline should be used at each scheduled assessment.

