
A. Assessment of Medical History will include, if known, baseline tumor characteristics: PD-L1 expression and Microsatellite Instability-High (MSI-H) status
 
B. Baseline imaging should be contrast-enhanced and include the following:
 

CT, PET-CT, and/or MRI of all suspected sites of disease within 28 days prior to study registration; for patients with a documented CT and/or MRI contrast allergy, the CT and/or MRI may be performed without contrast.

Brain (CT or MRI) within 1 year prior to study registration to screen for brain metastasis. In patients with known brain metastasis, brain imaging must be performed within 28 days prior to study registration.

 
Note: The imaging used at baseline should be used at each subsequent imaging time point.
 
C. Disease assessment by imaging and/or clinical examination. For patients with brain metastasis receiving SRS, disease assessment includes documentation of neurologic status and dosing history of steroids used for CNS edema management.
 
D. To determine if the patient is a candidate for SRT and if there is at least one lesion that will not receive SRT.
 
E. Consultation or, if the patient's treating medical oncologist is a VCU MCC sub-investigator, documentation that the patient is a candidate to continue PD-1 or PD-L1 inhibiting therapy.
 
F. Refer to Section 6.5.3.
 
G. Assessment to determine if AEs related to previous therapy have resolved or stabilized.
 
H. Chemistry includes the following panels and tests: basic metabolic panel (sodium, potassium, carbonate, chloride, glucose, calcium, BUN, and creatinine); hepatic panel (ALT, AST, ALP, total bilirubin, direct bilirubin, albumin, and total protein).
 
I. Only required for WCBP (see Section 4.1.12); if required, perform within 14 days prior to study registration. If SRT cannot begin within 14 days of a negative pregnancy test, the pregnancy test must be repeated prior to initiation of SRT. Serum or urine qualitative pregnancy test is acceptable.
	

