**Table 5 Footnotes:**

- A. Within +/- 1 week.
- B. Within +/- 2 weeks.
- C. Within +/- 4 weeks.
- D. Assessment and reporting limited to AEs that required discontinuation of the PD-1/PD-L1 inhibitor **and** steroid management.
- E. AEs will continue to be assessed every 2-6 months through end of year 2 in those who continue on PD-1 or PD-L1 inhibitor therapy in accordance with Section [6.7](#).
- F. Refer to Section [6.5.3](#).
- G. Serum chemistry includes the following panels and tests: basic metabolic panel (sodium, potassium, carbonate, chloride, glucose, calcium, BUN, and creatinine); hepatic panel (ALT, AST, ALP, total bilirubin, direct bilirubin, albumin, and total protein).
- H. After week 4, labs are done as part of routine care assessments, and these lab values are not required to be entered in eCRFs. They will be reviewed as part of AE assessments and, as applicable, AE eCRF entry.
- I. For WCBP, the pregnancy test must be repeated if the pre-entry test was performed more than 14 days prior to initiation of SRT. If required, either a urine or serum qualitative pregnancy test may be performed.
- J. The imaging (and/or clinical assessment) used at baseline should be used at each subsequent time point; refer to Section [10.1](#) for information regarding the response criteria to be used. For patients with brain metastasis receiving SRS, disease assessment includes documentation of neurologic status and dosing history of steroids used for CNS edema management.
- K. A goal of imaging at 8 weeks post-SRT is to rule out progressive disease.
- L. Imaging findings at the 24-week time point will be used for analysis of the primary endpoint (Section [13.3](#)). Refer to Section [10.3](#) regarding central review requirements. An optional disease assessment may be done at approximately 28 weeks (at least 4 weeks after the 24-week disease assessment) if needed to confirm response status.
- M. In the absence of post-SRT disease progression, continue with imaging and disease assessment every 2-3 months until 12 months following completion of SRT.
- N. In the absence of post-SRT disease progression, continue with imaging every 2-6 months until 2 years following completion of SRT. (If the patient has initiated a new cancer treatment, imaging is no longer required.)
- O. If the patient is available and willing to have a final blood sample collected for the correlative studies.

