## 13 STATISTICAL CONSIDERATIONS

### 13.1 Study Design

This is a single-arm phase 2 study of SRT and PD-1 or PD-L1 inhibiting therapy for patients with advanced solid tumors who achieved disease control during PD-1 or PD-L1 inhibiting therapy. The primary objective is to determine if SRT can restore the benefit of PD-1 or PD-L1 inhibiting therapy in patients with an advanced solid tumor who had disease control from PD-1 or PD-L1 inhibiting therapy but did not continue to improve. For patients enrolled with progression, this would mean SD, PR, or CR. For patients enrolled with stable or plateaued disease, restoration of benefit would be an objective response, ie PR or CR.

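### Section 10.2.2 requires follow-up imaging only of the original disease sites, and the calendar notes leave body coverage open, so undetected new lesions can bias the primary endpoint toward success

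*Combined protocol and SAP*

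**What the plan says.** - **Follow-up coverage.** Section 10.2.2 (Imaging): "Only imaging of the initial sites of disease is required at subsequent time points". The sentence gives its purpose as supplying measurements to judge antitumor effect. The next sentence adds: "The same type of imaging used at baseline should be used at each scheduled assessment".
- **Baseline coverage.** Table 4 footnote B, first bullet: "CT, PET-CT, and/or MRI of all suspected sites of disease within 28 days prior to study registration". The second bullet adds a brain CT or MRI within 1 year "prior to study registration to screen for brain metastasis", or within 28 days if brain metastases are known.
- **Repeat imaging in the calendars.** The Table 4 note: "The imaging used at baseline should be used at each subsequent imaging time point". Table 5 footnote J: "The imaging (and/or clinical assessment) used at baseline should be used at each subsequent time point".
- **Extra imaging.** Section 10.2.1: "At the investigator's discretion, additional assessments may be performed when clinically indicated".
- **What counts as success.** Section 3.3 sets the primary endpoint at 24 weeks by RECIST v1.1, plus RANO-BM if brain metastases are present. Section 13.1: "For patients enrolled with progression, this would mean SD, PR, or CR". Patients enrolled with stable or plateaued disease need PR or CR.
- **Decision rule.** Section 13.3 continues if at least 2 of 14 patients succeed, and calls for further study if at least 8 of 42 do.

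**The concern.** The required follow-up field is defined by where disease was at the start. A region that was suspected and scanned at baseline but found clear need not be scanned again under 10.2.2. If new disease appears there without symptoms, the week-24 read sees only the original lesions.

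Three routes lead from this to the primary endpoint:

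1. A patient enrolled with progression, whose measured lesions are stable, is scored SD and counts as a success.
2. A patient enrolled with stable disease, whose measured lesions shrink enough, is scored PR or CR despite new disease elsewhere. This should be less common, because SD alone is a failure in this group.
3. A patient whose early progression goes undetected, and who then has no 24-week assessment, is not evaluable under Section 13.5.2 and is replaced. A failure leaves the denominator.

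All three raise the observed rate. The trial is single-arm and judged against a fixed 10%, so no concurrent group carries the same error. The secondary irRC endpoint (Section 3.4.1) is exposed too, because Table 2 adds new measurable lesions to tumor burden.

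**Working it through.** **Inputs.** Null 10%, target 25%, 42 evaluable patients, 80% power and 5% level (Section 13.2). Continue if at least 2 of 14; positive if at least 8 of 42 (Section 13.3). Section 3.2 describes a different staging (11, then 41); the Section 13.3 rule is used here.

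**Formula.** For success probability p, P(positive) = sum over x = 2 to 14 of Bin(x; 14, p) × P[Bin(28, p) ≥ max(8 − x, 0)].

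**Reproducing the plan.**
- Stopping at stage 1 when p = 0.10: 0.9^14 + 14 × 0.1 × 0.9^13 = 0.2288 + 0.3559 = 0.585.
- Type I error at p = 0.10: 0.0464.
- Power at p = 0.25: 0.804.

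The stated 80% power and 5% level (one-sided) are met, with 0.05 − 0.0464 = 0.0036 to spare.

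**Adding false successes.** The documents give no missed-lesion rate, so let e be an assumed number of percentage points of false success on top of a true 10%.

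| e (points) | p | P(positive) | P(stop at stage 1) |
|---|---|---|---|
| 0 | 0.10 | 0.0464 | 0.585 |
| 1 | 0.11 | 0.0731 | 0.534 |
| 2 | 0.12 | 0.1076 | 0.486 |
| 3 | 0.13 | 0.1501 | 0.440 |
| 5 | 0.15 | 0.2552 | 0.357 |

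In patients, e = 1 is 42 × 0.01 = 0.42 expected false successes and e = 2 is 42 × 0.02 = 0.84. Less than one misread patient on average is enough to pass 10%.

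**What e implies for missed lesions.** Let f be the share enrolled with progression and q the share of that group's true failures read as SD, with a true 10% rate in both groups. Then p = 0.10 + 0.90 × f × q. Both f and q are assumed.

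| f | q | p | P(positive) |
|---|---|---|---|
| 0.25 | 0.05 | 0.1113 | 0.0769 |
| 0.50 | 0.02 | 0.1090 | 0.0700 |
| 0.50 | 0.05 | 0.1225 | 0.1175 |
| 0.50 | 0.10 | 0.1450 | 0.2267 |

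With f = 0.5, e = 1 needs q = 0.01 / 0.45 = 2.2%, and e = 2 needs q = 0.02 / 0.45 = 4.4%. The replacement route and false PR or CR are not included in these figures.

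**The case against.** The best defence is that 10.2.2 sets a minimum, for measurement only. Wider imaging is allowed at discretion (Sections 10.2.1 and 12), nothing tells readers to ignore a new lesion they see, and a scan of an involved site usually shows its surroundings. This is fair and limits the gap to regions not scanned. It does not close the gap: discretionary imaging depends on a clinical prompt, and central review (Section 10.3) covers CR, PR and SD cases without any instruction to obtain scans of other regions.

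A reader might also infer more than the text supports:

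- **That 10.2.2 contradicts the calendar.** The Table 4 note and footnote J name no body regions. Read as modality, in line with the second sentence of 10.2.2, they can be met together with it. What is established is an ambiguity. On the modality reading, nothing requires uninvolved regions to be scanned again.
- **That RANO-BM shows the gap.** RANO-BM applies where brain metastases are present, and there the brain is already an initial site. The criterion at issue is RECIST v1.1, which Section 10.1 adopts by citation without reproducing its new-lesion rule.
- **That a missed lesion always turns a failure into a success.** It may instead lead to replacement, or change nothing if a patient enrolled stable is scored SD.
- **That the type I error is 7% or 11%.** Those figures follow from assumed rates. They also take the 10% benchmark to have had full detection of new lesions, and the documents do not describe imaging coverage in the studies behind it.
- **That practice differs between sites.** SRT and on-study inhibitor doses are given at one center, so the documents do not support this. Any variation would be by patient and investigator.

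**Conclusion.** The point holds as a gap in required coverage plus an unclear instruction in the calendars. Section 10.2.2, followed exactly, allows new disease outside the original sites to go undetected, and no other section reliably prevents this. The direction is toward success. The size cannot be found from the documents: an assumed 1 to 2 points of false success takes the exact type I error from 4.6% to between 7.3% and 10.8%, and the design has almost no slack to absorb even the smaller figure. The conclusion assumes that a new lesion counts as progression under the adopted RECIST v1.1. The weakness should be corrected, but it does not invalidate the design.

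**What to change.** 1. In Section 10.2.2, replace the sentence limiting required imaging to the initial sites. State that the scheduled assessments at weeks 8, 16 and 24 repeat, by the same modality, the body regions covered by the baseline disease-assessment imaging (Table 4 footnote B, first bullet).
2. Reword the Table 4 note and Table 5 footnote J so that both say the same and name coverage as well as modality.
3. State that the one-time brain screening scan is not part of this repeat for patients without brain metastases. Without this line, a literal repeat of all baseline imaging would add brain scans at three visits for those patients.

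No extra new-lesion rule is needed, because RECIST v1.1 and RANO-BM are already adopted. Sample size, decision rule and visit schedule stay as they are. The cost is somewhat wider scan fields for patients whose follow-up would otherwise cover only involved sites. Regions never imaged at baseline, and the brain in patients without brain metastases, would still be scanned only when clinically indicated; that limit should be acknowledged in the report.
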